The study population for this research will consist of participants from:

Only at MDACC

Estimated Accrual:

Total Accrual at MDACC:33Estimated monthly accrual at MDACC:0-1

Accrual Comments: An average monthly accrual is about 0-1.

Is this an NCI-Cancer Therapy Evaluation Protocol (CTEP)?	No
Is this an NCI-Division of Cancer Prevention Protocol (DCP)?	No

Statistical Considerations:

This is a phase II study, single arm evaluating the efficacy and safety of dovitinib. The treatment plan consists in continuous treatment of dovitinib 500 mg PO daily 5 days on and 2 days off.

The primary endpoint is the six-month overall response rate (ORR) defined as the percentage of patients experiencing stable disease, complete or partial response (SD, CR or PR) as defined by RECIST. A response is anyone who experiences SD, CR or PR in the first 6 months. In other words, any patient that has not achieved either SD, CR or PR in the first 6 months will be considered a treatment non-responder. The trial will be conducted by the Simon's two-stage design using the mini-max criterion and the response rate will be estimated accordingly.

It is assumed that dovitinib will have a target ORR of 30%. An ORR of 10% or lower is considered a failure based on the typical ORR with a second line regimen for IBC and the new regimen will be rejected under this circumstance. When the probability of accepting a "bad" regimen (i.e. response rate 10%) is 0.05 and the probability of rejecting a "good" regimen (i.e. response rate 30%) is also 0.10, Simon's design to minimize the maximum sample size requires 22 patients in the first stage. If two or less patients respond to the treatment, the trial will be stopped and the regimen will be declared as ineffective. If at least three of the first 22 patients respond to the treatment, 11 additional patients will be entered in the study to reach a total of 33 patients. By the end of the study, the new regimen will be rejected if response rate is less than or equal to 6 out of 33 patients and will be accepted otherwise. Patient accrual will be suspended in the case when there are not at least 3 responders in the first 22 patients and not all 22 patients have been evaluated for 6 months. The operating characteristics of the trial are given as follows. When the true response rate is 0.10, the probability of stopping the trial early is 62.0%. On the other hand, if the true response rate is 0.30, the probability to stop the trial early is 2.1%. The expected sample sizes are 26.18 and 32.77 when the true response rates are 0.10 and 0.30, respectively. At the end of the study, the overall response rate and the

Yes

95% confidence interval will be reported and the toxicity profile of the regimen will be summarized.

As a secondary analysis we will evaluate safety by grading each adverse event (e.g., neutropenia, neurotoxicity, and CINV) according to CTCAE v4.0 and reporting the type, frequency and severity. In order to understand the relationship of FGF R1, FGF9, FGF, and VEGF-R1 signaling in serum and those in the tumor tissue (primary tumor or metastasis) with tumor growth, a correlation analysis of the expression levels of the biomarkers and tumor size will be conducted. For each biomarker, baseline expression level (EB) and post-treatment expression level (EP) will be determined by Immunohistochemistry (IHC). Pearson product-moment correlation coefficient measuring the linear relationship between the percent change in expression level, [EB-EP]/EB, and the percent change in tumor size as measured by CT scan will be reported along with the associated 95% confidence interval and the p-value for testing that the true linear correlation coefficient is non-zero. A linear model will be used to assess the joint impact of down regulation of FGFR-R1 and VEGF-R1 on tumor growth. The change in the number of circulating tumor cells (CTC) at baseline as compared to the number post-dovitinib will be investigated using a paired t-test. If the change in CTC is not normally distributed based on Shapiro-Wilk test, we will consider a robust non-parametric procedure such as the Wilcoxon Rank-Sum test.

Data Safety Monitoring Board / DSMB at MDACC:

Select the name of the data safety monitoring board (DSMB) monitoring this protocol: Not Applicable

Please explain: This is not a randomized and not blinded study.

Protocol Monitoring:

Does this protocol have a schedule for interim and final analysis?

Provide a summary or schedule of interim analysis.

We will conduct an interim analysis after the first 22 patients following Simon's 2 stage min-max design.

Protocol Monitoring Plan:

Adverse events will be assessed according to the CTCAE version 4.0. All study patients who have received any dose of dovitinib will be evaluable for safety. Unexpected adverse events including laboratory adverse events deemed clinically significant by the investigator will be graded and recorded.

The ongoing review of safety data will include review of clinical AEs and SAEs. The NCI-CTC version 4.0 will be used to grade all AEs. An AE is an undesirable medical occurrence (sign, symptom, or diagnosis) or worsening of a pre-existing medical condition (diabetes, congestive

heart failure, rheumatoid arthritis) that occurs after initiation of investigational product whether or not considered to be investigational product related. A worsening of an existing medical condition is one that was present at baseline (e.g., cancer, diabetes, migraine headaches, gout) and became more severe, more frequent, or increased in duration during investigational product treatment.

Reporting Procedures for AEs (>/=2 non-hematological and >/=3 hematological AEs) occurring after informed consent signing observed by the investigator or reported by the subject (whether or not attributed to investigational product), will be documented to the medical record then entered into the case report form. Abnormal laboratory values should not be reported as AEs; however, any clinical consequences of the abnormality should be reported as AEs. Hospitalization for elective surgery or routine clinical procedures that are not the result of an AE (e.g., surgical insertion of central line) need not be considered AEs and should not be recorded as an AE. Disease progression should not be recorded as an AE. The Investigator is responsible for verifying and providing source documentation for all adverse events and assigning attribution for each event for all subjects enrolled on the trial.

All patients will be followed for safety 30 days (+/- 10 days) after the last dose of dovitinib, and every 3 months for duration of up to one year or until death, whichever occurs first for response, PFS and OS. Patients will be followed a minimum of every 3 months by clinic visit (at MD Anderson or a local physician), telephone or e-mail correspondence.

Intellectual Property:

1. Does this study include any agents, devices, or radioactive compound (or No drug) manufactured at MD Anderson Cancer Center or by a contract manufacturer?

Investigational New Drugs (IND):

Does this protocol require an IND? Yes

Who is the IND Holder/Regulatory Sponsor? MDA IND Number: Pending

Please "Compose" an Investigator's Brochure Cover Letter. For technical assistance, contact the PDOL Help Desk, [contact].

No

Investigational Device (IDE):

Does this study utilize an Investigational Device?

Sponsorship and Support Information:

Does the Study have a Sponsor, Supporter or Granting Agency? Yes

Sponsor Name: Novartis Support Type: Industry Funding

This Sponsor/Supporter/Granting Agency will receive data.

Radioactive Material:		
Does this study involve the administration of radioisotopes or a	No	
radioisotope labeled agent?		
Click here for help		

Biosafety:

Does this study involve the use of Recombinant DNA Technology?	No
Does this study involve the use of organisms that are infectious to humans?	No
Does this study involve human/animal tissue other than blood derived hematopoietic stem cells?	No

Questions should be addressed to the Transfusion Medicine Tissue Coordinator at [contact].

Laboratory Tests:

Is there any biomarker testing in this study being used to determine patient/participant eligibility, treatment assignment, or management of patient/participant care?

• Yes

◯ No

○ Not Applicable For This Protocol

Please provide the name of the test(s), the purpose of the test, the performing laboratory identification and contact information, and confirm that the testing lab is CLIA certified (may attach a certificate or provide a certificate number).

HER2 status is the only one for determination of eligibility. IHC and FISH are both MDACC CLIA certified.

Other biomarkers FGFR-R1, VEGF-R1, Cytokines and Micro RNA, CTC, and EMT CTC are for research only.

Manufacturing:

Will you manufacture in full or in part (split manufacturing) a drug or biological No product at the M. D. Anderson Cancer Center for the proposed clinical study?

Student/Trainee Information:

Is this research being conducted as a partial fulfillment for completion of a degree? No

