The dose limiting toxicity (DLT) of dovitinib as single agent in patients with advanced cancer is being evaluated in 7 Phase I dose escalation studies. As of the 18 November 2009 cutoff date, 20 DLTs were observed in cycle 1 of dovitinib treatment. The DLTs included grade 3 anorexia/nausea/vomiting/diarrhea, grade 4 fatigue, grade 4 neutropenia, grade 3 hypokalemia, grade 2

sinus bradycardia, and delayed recovery from AST/ALT elevation, increased GGT, hypertensive.

Subsequently, dovitinib is being studies as a single agent in eight Phase I and one Phase II clinical trials designated to characterize safety, tolerability, pharmacokinetics (PK), phamacodynamics (PD) and anti-tumor activity.

Additionally, in one study, 3 DLTs were reported by the investigators beyond cycle 1 treatment, including a grade 3 hypertension (occurred on cycle 2 day 8 in 1 patient at 100 mg/day), a grade 3 anorexia (occurred on cycle 2 day 9 in 1 patient at 175 mg/day), and a grade 3 alkaline phosphatase increase (occurred on cycle 2 day 29 in 1 patient at 175 mg/day).

There are four studies that were terminated prior to reaching the maximum tolerated dose (MTD). The MTD for continuous daily dosing regimen was defined at 400 mg; the MTD for 5 days on/2 days off dosing regimen was defined at 500 mg. Based on previous phase I safety data, and ongoing study for metastatic breast cancer, we propose a 500 mg daily 5 days on/2 days off schedule for this study.

Eligibility: (List All Criteria)

Inclusion:

1) Patients have histological confirmation of breast carcinoma with a clinical diagnosis of IBC based on presence of inflammatory changes in the involved breast, including diffuse erythema and edema (peau d orange), with or without an underlying palpable mass involving the majority of the skin of the breast. Pathological evidence of dermal lymphatic invasion should be noted but is not required for diagnosis.

2) Patients have stage IV disease with local or distant relapse

3) Patients have negative HER2 expression by IHC (defined as 0 or1+), or FISH. If HER2 is 2+, negative HER2 expression must be confirmed by FISH.

4) Patients are able to swallow and retain oral medication.

5) Patients have ECOG performance status 0-2.

6) Patients have received two or more standard chemotherapies for metastatic disease and have relapsed.

7) Patients have ability and willingness to sign written informed consent.

8) Patients are 18 years of age or older.

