9) Female patients of childbearing potential (A female not free from menses > 2 years or not surgically sterilized) must be willing to use highly effective contraception to prevent pregnancy or agree to abstain from heterosexual activity throughout the study. Highly effective contraception, defined as male condom with spermicide, diaphragm with spermicide, intra-uterine device. Highly effective contraception must be used by both sexes during the study and must be continued for 8 weeks after the end of study treatment. Oral, implantable, or injectable contraceptives may be affected by cytochrome P450 interactions, and are therefore not considered effective for this study.

10) Female patients of childbearing potential must have negative serum pregnancy test </=14 days prior to starting study treatment.

11) If Patients have been treated with anti-VEGF agents, such as Bevacizumab, last dose must be > 4 weeks.

12) Patients have biopsy tissue of the metastatic disease (including chest wall or regional nodes) available (paraffin blocks or up to 20 unstained slides), if no biopsy tissue available, a biopsy (or thoracentesis if patient has pleural effusion only) of the metastatic disease will be performed to confirm the diagnoses.

13) Serum total bilirubin must be within Upper Limited Normal (T. Bilirubin ULN=1.0 mg/dl)

14) AST and ALT must be < 2.5 x ULN(with or without liver metastases).

Exclusion:

1) Patients are receiving concurrent anti-cancer therapy (chemotherapy, immunotherapy, radiation therapy and biological therapy) while taking study medication.

2) Cirrhosis of liver, or known hepatitis B or C infection have hepatic impairment Child-Pugh Score of B or worse.

- 3) ANC < 1.5
- 4) Patients have an active infection and require IV or oral antibiotics.

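### The exploratory biomarker correlation has no stated rule for a baseline IHC value of zero, and a Pearson coefficient alone leaves it open to one low-baseline patient, in either direction

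*Combined protocol and SAP*

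**What the plan says.** The analysis is described in the paragraph of Statistical Considerations that begins with the secondary safety analysis. For each marker, "baseline expression level (EB) and post-treatment expression level (EP) will be determined by Immunohistochemistry (IHC"). The change score is the "percent change in expression level, [EB-EP]/EB", so a fall in expression is positive. It is related to percent change in tumor size on CT by a Pearson coefficient, with a 95% confidence interval and a p-value for a non-zero correlation. Next comes a joint model: "A linear model will be used to assess the joint impact of down regulation of FGFR-R1 and VEGF-R1 on tumor growth". The scale of its predictors is not stated.

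The same paragraph gives the circulating tumor cell (CTC) comparison a safeguard: "If the change in CTC is not normally distributed based on Shapiro-Wilk test, we will consider a robust non-parametric procedure". No such safeguard is given for the IHC correlation. The text also gives no IHC scoring scale, no minimum baseline value, no rule for a baseline of zero and no influence check.

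No eligibility criterion requires FGFR-R1 or VEGF-R1 expression. The only place where an IHC reading of zero appears is Inclusion 3, for a different marker: "negative HER2 expression by IHC (defined as 0 or1"+). Laboratory Tests sets the status of this work: "Other biomarkers FGFR-R1, VEGF-R1, Cytokines and Micro RNA, CTC, and EMT CTC are for research only".

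**The concern.** Two properties of the score matter. First, it divides by the baseline value, so a marker-negative baseline gives no number. The plan does not say what then happens. The natural inference is that the pair is left out, and a reader of the results would not know how many were. If the joint model uses the same score, a zero on either marker would remove the patient from it.

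Second, the score is lopsided. A complete loss of expression scores +1, while a rise from a low baseline can score far below -1. A Pearson coefficient on few pairs is sensitive to one such point. The study calendar makes the biopsy before cycle 3 optional, so there may be well under 33 pairs. At stake is how a published exploratory coefficient is read: it could largely reflect one patient, with nothing beside it to show this.

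**Working it through.** The documents state no figure for the biomarker correlation, so there is none to reproduce. The inputs taken from the documents are the score formula, the Pearson coefficient and the maximum of 33 patients. All IHC values, spreads and correlations below are assumptions.

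**1. The score.** Let S = (EB - EP)/EB.
- EB = 0, EP = 50: -50/0, no value. EB = 0, EP = 0: 0/0, no value.
- EP = 0, any EB > 0: S = +1, the maximum.
- 1+ to 3+: (1 - 3)/1 = -2. On an ordinal scale ending at 3+ (an assumed top; Inclusion 3 names 0, 1+ and 2+), this is the lowest possible value.
- On a continuous scale: 20 to 60 gives -40/20 = -2, and 5 to 50 gives -45/5 = -9.

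**2. Leverage of one patient at S = -2.** Assume the other n - 1 patients have mean 0.2 and SD 0.4. Then h = 1/n + (x - mean)²/SSx, where SSx = (n - 2) × 0.4² + ((n - 1)/n) × 2.2².

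For n = 20: mean = (19 × 0.2 - 2)/20 = 0.09; SSx = 18 × 0.16 + 0.95 × 4.84 = 7.478; h = 0.05 + 2.09²/7.478 = 0.63.

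| n | h | average leverage 2/n |
|---|---|---|
| 12 | 0.76 | 0.17 |
| 20 | 0.63 | 0.10 |
| 33 | 0.50 | 0.06 |

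Varying the SD from 0.2 to 0.8 gives 0.87 to 0.32 at n = 20 and 0.80 to 0.22 at n = 33.

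**3. Effect on the coefficient.** Simulation with 8,000 replicates: the others' scores are normal (mean 0.2, SD 0.4) capped at 1, and their tumor change is correlated 0.6 with the uncapped score. One patient is then added at S = -2 or -9. That patient's tumor change is either unrelated to the score or on the same line as the others with the same scatter.

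| n, score | Pearson, others only | unrelated | same line | Spearman, others only | unrelated | same line |
|---|---|---|---|---|---|---|
| 20, -2 | 0.59 | 0.35 | 0.76 | 0.56 | 0.50 | 0.62 |
| 20, -9 | 0.59 | 0.11 | 0.97 | 0.56 | 0.50 | 0.62 |
| 33, -2 | 0.59 | 0.41 | 0.72 | 0.57 | 0.53 | 0.60 |
| 33, -9 | 0.59 | 0.14 | 0.95 | 0.57 | 0.53 | 0.60 |

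Spearman moves by 0.06 or less in either direction. It does not cure the zero-baseline problem, because it uses the same score.

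**4. How often one patient holds over half of the score's variance.** This was simulated with 6,000 replicates over five assumed baseline distributions on a continuous scale up to 300 and three models of change (additive, log-normal ratio, fractional fall). At n = 33 the range is 0% to 44% for the planned score and 0% to 13% for absolute change EB - EP. At n = 12 it is 4% to 41% and 7% to 41%. Every baseline set has a floor of at least 1, so these figures say nothing about how often EB = 0.

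**5. False positives.** With no true association, using the first of the baseline sets, Pearson rejects in 4.9% to 5.5% of replicates and Spearman in 4.8% to 5.5%.

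**The case against.** The strongest reply is that nothing here changes a decision. The markers are exploratory and for research only, and neither the Simon design nor the response rate uses them. That stands, and it limits the point to an optional improvement.

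Second, the frequency is unknown. The zero reading is borrowed from HER2, and scores below -2 need a continuous scale that the documents do not mention. That also stands: the table rows for -9 and the variance shares illustrate what could happen, and do not predict it.

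Third, leverage is not error. A low-baseline patient who follows the common relation strengthens the correlation legitimately. This is right, which is why both directions are shown. It does not remove the reason to print a rank coefficient beside Pearson, since the reader needs to see when the two disagree.

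Fourth, fractional fall is a natural measure of down-regulation, and a tumor with no expression cannot be down-regulated, so leaving it out may suit the question. Absolute change is not uniformly steadier either. Under fractional change, with the first of the baseline sets, one patient dominates the planned score in 5%, 0.3% and 0% of replicates at n = 12, 20 and 33, against 41%, 26% and 11% for absolute change. This is a good reason to keep the planned score as the main one. It is not a reason to leave the exclusion unstated and uncounted.

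**Conclusion.** The point holds as a low-cost improvement to an exploratory analysis. That the score has no value at EB = 0 is arithmetic. That one low-baseline patient can move Pearson r materially is shown under stated assumptions: at n = 20 and a score of -2, from about 0.59 to 0.35 or to 0.76, against 0.50 to 0.62 for Spearman.

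Four stronger readings are tempting, and the documents do not support them.
- A reader might infer that a known share of patients will be lost. No marker scale or baseline distribution is given, and exclusion at EB = 0 is itself an inference from silence.
- A reader might infer that the coefficient is pulled towards zero. That follows only if the extreme patient's tumor change is unrelated to the score.
- A reader might infer that the p-value is unreliable. The simulated null rejection rate stays near 5%.
- A reader might infer from Inclusion 12 that stored tissue predating other therapy serves as the baseline. That criterion concerns confirming the diagnosis, and the calendar footnote on baseline tissue is garbled in the available text. It would in any case be a separate question of timing.

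**What to change.** Keep the planned Pearson analysis of the ratio score as the main analysis, and add:

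1. Spearman's coefficient with its 95% confidence interval, reported beside Pearson for each marker. The Bonett-Wright interval covered 95.5% to 96.6% at zero correlation in the simulations.
2. A statement that pairs with EB = 0 are excluded from the ratio score, with their number reported for each marker and, if the joint model uses the ratio, for that model too.
3. A supportive analysis of absolute change, EB - EP, which has the same sign as the planned score, over all pairs including EB = 0, in both the correlation and the linear model.

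The cost is a few sentences and slightly more exploratory output. All three items use only data that the plan already collects, so they can be applied at reporting even though the title page marks the protocol as terminated; if so, they should be labelled as added later. Absolute change should stay supportive. It answers a somewhat different question, a patient with EB = 0 can score only zero or a rise, and it can be the less stable score when change is fractional.

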MDAnderson Cancer Center

Protocol Abstract Page

A Phase II Study of TKI258 (Dovitinib Lactate) as Salvage Therapy in Patients with Stage IV HER2-negative IBC and Local or Distant Relapse 2010-0296

Study Chairman:	[name]
Department:	Breast Medical Oncology
[contact]
Unit:	1354
Full Title:	A Phase II Study of TKI258 (Dovitinib Lactate) as Salvage Therapy in Patients with Stage IV HER2-negative IBC and Local or Distant Relapse
Protocol Phase:	Phase II
Version Status:	Terminated 06/08/2018
Version:	19
Document Status:	Final

Core Protocol Information

Abstract

Objectives:

Primary

To determine an overall response (complete response [CR], partial response [PR] or stable disease [SD]) of dovitinib in patients with HER2-normal, local or distant relapse of metastatic inflammatory breast cancer

Secondary

• To evaluate safety analysis measures in terms of type, frequency and severity of adverse event reactions reported according to CTCAE v4.0

Exploratory Biomarkers:

• To explore the predictive values of baseline FGFR-R1, and VEGF-R1, signaling in tumor tissue (primary tumor or metastasis) before and during treatment with dovitinib.

• To determine the effect of dovitinib on the presence of CTC and CTCs with epithelial and/or EMT gene expression in PB.

• To collect and archive biopsy tumor tissue, serum and plasma for later hypothesis generating

associations

Rationale: (Be as concise as possible)

Inflammatory breast carcinoma (IBC) is one of the most aggressive forms of primary breast carcinoma that accounts for 1-6% of all invasive breast tumors in the United States and Western Europe. IBC is distinguished from other types of breast cancer by clinical, pathologic and molecular features. Additional pathologic characteristics of IBC include high grade, negative hormone receptor status and overexpression of HER2 and E-cadherin; all of which are poor prognostic factors. Molecular features of IBC include mutation of the p53 suppressor gene, and an increased expression of proangiogenic factors (basic fibroblast growth factor [bFGF], vascular endothelial growth factor [VEGF], interleukin [IL]-6 and IL-8).

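### The only fallback named for the before/after CTC comparison is the Wilcoxon rank-sum test, which is for independent samples, but the counts are paired

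*Combined protocol and SAP*

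**What the plan says.** The exploratory objectives include this aim: "To determine the effect of dovitinib on the presence of CTC". The analysis is set out at the end of Statistical Considerations, in three steps.

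- **Quantity compared:** "The change in the number of circulating tumor cells (CTC) at baseline as compared to the number post-dovitinib".
- **Default test:** this "will be investigated using a paired t-test".
- **Fallback:** "If the change in CTC is not normally distributed based on Shapiro-Wilk test", then "we will consider a robust non-parametric procedure such as the Wilcoxon Rank-Sum test".

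The same section describes the design: "This is a phase II study, single arm evaluating the efficacy and safety of dovitinib". The schedule table marks blood collection at screening and at cycle 3, so each patient can supply two samples. No signed-rank test, sign test or other paired non-parametric method appears anywhere in the document.

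**The concern.** The default test and the normality check both work on the within-patient change. The named fallback does not. The rank-sum (Mann-Whitney) test pools the two sets of counts, ranks them as if they came from two unrelated groups, and discards the information about which counts belong to the same patient. A single-arm trial has no second independent group to which it could apply.

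The consequence is a p-value with the wrong reference distribution. If a patient's two counts are positively correlated, the test rejects too rarely and can miss a real change. If they are negatively correlated, it rejects too often. The plan names no other hypothesis test for the CTC objective, so the choice bears directly on what is reported for it.

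**Working it through.** **Inputs from the documents.** One arm. CTC measured at baseline and after treatment in the same patients. Default paired t-test, with Shapiro-Wilk on the change. At most 33 patients, or 22 if accrual ends at stage 1 ("If two or less patients respond to the treatment, the trial will be stopped"). These are ceilings on the number of pairs, because a patient without the cycle 3 sample contributes none. The plan states no power, alpha, SD, correlation or effect size for CTC, so it has no figure to reproduce.

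**Step 1: why the rank-sum p-value is off.** For n pairs, the rank-sum statistic behaves in large samples like the mean of F(X) - F(Y), where F is the common distribution of the counts when nothing changes. F(X) and F(Y) are uniform with variance 1/12, so each pair contributes variance (2/12)(1 - r_S), where r_S is the rank (Spearman) correlation. The test assumes 2/12. The variance ratio is therefore 1 - r_S, and the actual two-sided type I error at nominal 5% is

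2 × [1 - Φ(1.96 / √(1 - r_S))].

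If the log counts are bivariate normal with correlation ρ, then r_S = (6/π) arcsin(ρ/2). For ρ = 0.5: r_S = 0.483, √(1 - 0.483) = 0.719, 1.96/0.719 = 2.725, and the error is 0.6%. For ρ = -0.3: r_S = -0.288, √1.288 = 1.135, 1.96/1.135 = 1.727, and the error is 8.4%.

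**Step 2: simulation at the trial's size.** All of these inputs are assumptions:

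- log SD 1.2;
- log shift 0 for type I error and -0.6 for power (exp(-0.6) = 0.55, a 45% fall in the median rate);
- 22 or 33 pairs;
- continuous log-normal values, or Poisson counts around log-normal rates with median 5 (9% zeros) or 1 (39% zeros);
- two-sided 0.05, with 10,000 replicates per setting.

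Ranges run over the two sample sizes and the three count models.

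| Log-scale correlation | Rank-sum type I error, formula | Rank-sum type I error, simulated | Power lost by using rank-sum (points) |
|---|---|---|---|
| -0.3 | 8.4% | 6.6-8.3% | not comparable (rank-sum exceeds 5%) |
| 0 | 5.0% | 4.6-5.1% | none (rank-sum level or up to 7 better) |
| 0.3 | 2.0% | 2.0-3.3% | 4-7 |
| 0.5 | 0.6% | 0.7-2.4% | 9-20 |
| 0.7 | 0.05% | 0.1-1.3% | 16-43 |

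Signed-rank type I error stays at 4.4-5.4% throughout. Poisson noise weakens the correlation between the observed counts, so the count models lie nearer to 5% than the formula does.

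Power at correlation 0.5, signed-rank vs rank-sum:

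| Pairs | Log-normal | Median rate 5 | Median rate 1 |
|---|---|---|---|
| 33 | 69% vs 49% | 58% vs 40% | 38% vs 25% |
| 22 | 49% vs 30% | 41% vs 25% | 26% vs 17% |

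**Step 3: a different model and fewer pairs.** With Poisson-lognormal counts of log-mean 1.5, log SD 1.2, shift -0.5 and correlation 0.5 (4,000 replicates), power for signed-rank vs rank-sum is 44% vs 26% with 33 pairs, 31% vs 17% with 22, and 23% vs 12% with 15. The pattern is the same.

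**Step 4: would the fallback be reached?** Under the Step 2 models, Shapiro-Wilk at an assumed 0.05 level rejects normality of the change in about 70-97% of data sets. On those assumptions the fallback would usually be the test reported.

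**The case against.** The strongest reply is that the plan does not commit to the rank-sum test. Its wording is permissive and offers the test only as an example. The surrounding sentences are plainly paired, so this may be a naming slip for signed-rank, and an analyst could choose signed-rank without departing from the text. That is fair. But the one test named is unsuitable, nothing elsewhere corrects it, and an analyst who takes the name literally would run the wrong test.

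Three further points stand as limits:

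- **The remedy is not unique.** A sign test, a paired permutation test or a paired t-test on transformed counts would also respect the pairing. Signed-rank is the direct counterpart of the planned t-test.
- **The size is unknown.** It depends wholly on assumed inputs and runs from no loss to 43 points of power. With sparse counts the loss is smaller in points, and both tests are weak.
- **Inflated false positives need negative correlation,** for which the documents give no basis. With positive correlation the harm is a missed effect.

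The stakes are also low. The Laboratory Tests section says "Other biomarkers FGFR-R1, VEGF-R1, Cytokines and Micro RNA, CTC, and EMT CTC are for research only".

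That the fallback runs only if normality is rejected is true, but it helps little given the trigger rates in Step 4.

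**Conclusion.** The concern holds, at minor severity. That the named test does not fit the design follows from the text alone and needs no assumption. How much harm it would do is conditional. It is nil if the two counts are uncorrelated. At a log-scale correlation of 0.5, under the models above, rank-sum type I error falls to 0.7-2.4% and 9-20 points of power are lost. The effect is confined to an exploratory CTC result. The primary endpoint, the Simon two-stage rule, the sample size and patient management are not affected.

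**What to change.** In the last sentence of the CTC analysis in Statistical Considerations, replace the Wilcoxon rank-sum test with the Wilcoxon signed-rank test on within-patient differences. No other change is needed to correct the error.

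The cost is one phrase. Data collection, sample size and conduct stay as they are. The document is marked as terminated, so the correction matters for how any CTC result is analysed and reported.
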